6.3 Methods of Minimising Bias

6.3.1 Randomisation

The active and maintenance treatment phase consists of a 1:1 randomized placebo-controlled allocation sequence for the 36-week study period. A dynamic computerized 1:1 randomisation stratified for age, gender, type of treatment (in- or outpatient) and hsCRP across each site will be applied. A minimisation algorithm integrated in SecuTrial® will provide a balanced distribution between the two treatment groups (active/ placebo) for each site and strata.

Access to the SecuTrial® generated randomisation list will be restricted to the Clinical Trial pharmacist, in case of an interim analysis to the IDMC, upon request to the regulatory authorities

and to the data management at the USZ CTC. The study medication will be labelled at the KAZ and will be sent out to the study sites in two batches.

The algorithm and allocation process is implemented in SecuTrial and the development of the algorithm is done by the data manager of the Clinical Trial Centre and cannot be influenced by the investigators. The clinicians and researchers who enrol the patients just provide the relevant stratification data. The minimization algorithm contains an element of chance so that even with the knowledge of all previous allocations the next allocation cannot be determined.

Participants, parents, treating clinicians and doctors, research assistants, all involved researchers including the PI remain blind to the allocation of participants to the study drug (active/ placebo). SecuTrial® only provides one single randomisation number making it impossible to guess the allocation. Data analyst (PD Dr. rer. nat. [name], [name]) will only get access to the randomisation code list after completion of data entry, double entry of a subset of data and final closure of the database. The only person who has access to the computer-generated allocation code is the data manager of the CTC and the clinical trial pharmacist of the Clinical Trials Pharmacy of the Universities of Zürich (*Kantonsapotheke Zürich KAZ*).

If deemed necessary, the IDMC is allowed to review unblinded data as further specified in the IDMC SOP.

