11.4 Planned Analyses

All analyses will be carried out after closure of the database to avoid unblinding with the exception of baseline data, which might be exported previously for master and PhD projects. All randomized patients will be included in the model, and the efficacy of omega-3 fatty acids on depressive symptoms will be analyzed using a linear random coefficient regression model, as described below.

Furthermore, we will compare the scores between baseline and end of study (week 36) for all the different scales and questionnaires, which were assessed previously. Additionally, cognitive functioning will be compared between the beginning of the study and its end while controlling for the effect of depressive symptoms on cognitive outcome measures. An SAP will describe all planned a priori analysis.

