6.2 Difference in Proportion of Responders

A two-proportion z-test would require 97 participants per treatment arm to have 80% power to detect a difference in response of 20% (with 60% response in the treatment group and 40% response in the control group) at the 0.05 two-sided significance level. Accounting for a 10% loss to follow-up results in a total sample size of 216 participants.

7 Statistical analyses

Analysis sets The following analysis sets are defined in accordance with the ICH-E9 guidelines:

- The full analysis set (FAS) includes all randomized subjects. The FAS will be used for 'as randomized' evaluation. Only in exceptional cases may subjects be excluded from the FAS. In such cases the reason for exclusion will be justified and documented.
- The safety analysis set includes all randomized subjects receiving at least one dose of randomized treatment. The safety analysis set will be used for 'as treated' evaluation.

Baseline comparability of randomized groups Baseline descriptive variables of participants (including antidepressant use) will be summarized overall and by treatment arm using suitable measures of central tendencies and variability for continuous data (means or medians, SD or IQR) and frequencies and proportions for categorical data. No hypotheses are tested.

The number of participants lost to follow-up, initiating antidepressants, and adhering to the protocol will each be tabulated by treatment arm and visit. Baseline characteristics will also be summarized across the groups of participants completing the trial, lost to follow-up, and initiating antidepressant use.

General statistical considerations Statistical analysis results will generally be presented as point estimates with two-sided 95% confidence intervals. A limited number of analysis results will additionally be reported with p -values, which will be interpreted as indicative of superiority when the value is less than 5% and the estimated treatment contrast favors the omega-3 treatment arm.

Descriptive statistics for all efficacy and safety endpoints will be presented according to treatment arm.

The baseline values are collected at visit 1 (0 weeks), which is the first week after the lead-in phase. Further measurements are taken at visits 2 through 5 at 6, 12, 24, and 36 weeks.

The clinical trials registry number (03167307) will be used as a seed number, if needed.

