Missing data By design, several baseline model covariates cannot be missing, as they are required for minimization during randomization. We distinguish between study dropouts and intervention dropouts. Study dropouts are participants whom withdraw consent, are monotone not available for follow-up visits, or are removed from the trial according to the protocol due to non-compliance (< 60% pills taken). Intervention dropouts are participants whom newly initiate an off-trial antidepressant or are newly prescribed an increased dose of an off-trial antidepressant prescribed before baseline.

Methods to handle missing data are outlined per analysis type below. Where multiple is used, 50 imputed datasets will be computed. Results across datasets will be combined using Rubin's rule.

Modeling In case of covariate imbalance on baseline covariates other than antidepressant use, omega-3 index, age, gender, and hsCRP, these covariates will also be included in the models described below. In case of computational convergence issues, simpler models will be estimated.

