where time t is considered a factor (while also investigating possibility of linearizing time effect) and randomized treatment group (intervention) and the interaction between randomized treatment group and time are included as fixed effects. The baseline values of the minimization factors age, gender, and hsCRP, as well as baseline antidepressant use and omega-3 index are included as covariates. The baseline outcome measure is modeled in the response, not as a covariate. The terms b_{i0} , b_{i1} , and b_{s0} represent participant-specific random intercepts and slopes and site-specific random intercepts. The random effects are assumed to be normally distributed and an unstructured covariance matrix will be assumed. The error term $\varepsilon_i(t)$ is assumed to be normally distributed with mean zero and variance σ^2 , independent of the random effects and is independent over time. An overall treatment effect for CDRS-R score at 36 weeks ($\beta_1 + \beta_{11}$) will be reported with a 95% confidence interval and corresponding p -value.

The competing survival models for time to event r (intervention dropout or study dropout) take the form:

$$\lambda_{ir}(t) = \lambda_{0r} \exp\{\gamma_1 \text{intervention} + \alpha_r m_i(t)\}$$

where the cause-specific Cox models include intervention as a time-independent effect and the estimated true trajectory of CDRS-R as a time-varying effect. The parameters α_r measure the strength of association between the longitudinal outcome and risk of the corresponding dropout event.

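### The SAP adds further baseline covariates to the adjusted models when they look imbalanced, without defining imbalance, so the final covariate set of the primary model is not pre-specified

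*SAP*

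**What the plan says.** The primary joint model in SAP 7.1 has a stated covariate list: "The baseline values of the minimization factors age, gender, and hsCRP, as well as baseline antidepressant use and omega-3 index are included as covariates". Site enters as a random intercept, and the reported contrast is β1 + β11, the arm difference at 36 weeks.

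The Modeling paragraph in SAP section 7 then opens that list. Its trigger reads "In case of covariate imbalance on baseline covariates other than antidepressant use, omega-3 index, age, gender, and hsCRP". The consequence it attaches to that trigger is that "these covariates will also be included in the models described below". The models that follow include the primary joint model and the log-binomial and ANCOVA models of 7.2.1. Neither document says how imbalance is measured, what size counts, which variables are candidates, or who decides.

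The baseline comparability paragraph of the same section provides the only view of imbalance: baseline variables "will be summarized overall and by treatment arm". It adds "No hypotheses are tested", so no p-value rule is implied.

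On timing, Protocol 6.3.1 states that the data analyst "will only get access to the randomisation code list after completion of data entry", the double-entry check and final closure of the database. Protocol 11.4 states: "All analyses will be carried out after closure of the database to avoid unblinding with the exception of baseline data". That exception covers baseline data, not allocation.

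**The concern.** The judgement of imbalance needs the arms, and the arms reach the analyst only when the outcomes are complete and locked. Nothing in either document separates the choice of extra covariates from sight of the results. Protocol 11.4 says the SAP will describe all analyses planned in advance, and Protocol 11.4.6 says anything else will be declared post hoc. A covariate set that is unknown until the arms are compared does not meet that standard.

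The method is also weak in its own right. In a randomised trial baseline imbalance is chance. A covariate earns its place by predicting the outcome or by having been used in the allocation, and imbalance indicates neither. In-/outpatient type shows the problem. SAP section 1 names it as a minimisation factor at sites offering both kinds of care, yet no model contains it, so it could enter only through the undefined trigger.

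The rule also fits poorly with neighbouring text:

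- Baseline CDRS-R is not among the five exceptions. Read literally, an imbalance would add it to the primary model, although 7.1 puts the baseline score in the response and not among the covariates.
- The imputation models in 7.1.2 and 7.2.1 are fixed lists, so an added covariate could be in the analysis model and not in the imputation model.
- A larger joint model makes the next rule more likely to apply: "In case of computational convergence issues, simpler models will be estimated". That rule has no stated order of simplification.

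At stake is the credibility of the primary estimate and p-value.

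**Working it through.** The plan gives no figure for this rule, so there is none to reproduce. Three questions can be checked.

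**1. How often would chance alone trigger the rule?**

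Inputs: 110 per arm (Protocol synopsis). The number of candidates k is assumed, as is independence between them.

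- Standard error of a standardised difference under randomisation: √(2/110) = 0.1348.
- Chance that one covariate exceeds cut-off c: 2 × [1 − Φ(c/0.1348)].
- Chance that at least one of k does: 1 − (1 − p)^k.

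| Cut-off | c/SE | p, one covariate | k = 5 | k = 10 |
|---|---|---|---|---|
| \|SMD\| > 0.1 | 0.742 | 0.458 | 95% | 99.8% |
| \|SMD\| > 0.2 | 1.483 | 0.138 | 52% | 77% |
| \|SMD\| > 0.25 | 1.854 | 0.064 | 28% | 48% |
| p < 0.05 | 1.96 | 0.050 | 23% | 40% |

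The p < 0.05 row is only a benchmark, since the SAP rules out baseline tests. Two things lower these rates:

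- Correlation. With a pairwise correlation of 0.5 (assumed) and k = 10, the rate is 29% at p < 0.05 and 61% at |SMD| > 0.2.
- A larger trial. Protocol 6.2 reports 225 randomised, 20 more needed and up to 20 extra, so at most 265, or 132.5 per arm. The standard error is then √(2/132.5) = 0.1229, p at |SMD| > 0.2 is 0.1035, and 1 − 0.8965^10 = 66.5%. The p < 0.05 row does not change.

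The answer ranges widely with a cut-off that the SAP does not state.

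**2. Does the rule inflate the type I error?**

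Simulation under no treatment effect: 110 per arm, two-sided 5%, a linear model, 20,000 replicates per scenario. Assumed: 5 or 10 independent candidates jointly explaining 10%, 20% or 30% of outcome variance.

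| Way of adjusting | Type I error across scenarios |
|---|---|
| All candidates, fixed in advance | 4.9-5.1% |
| Mechanical, \|SMD\| > 0.1 | 3.3-4.6% |
| Mechanical, \|SMD\| > 0.2 | 3.6-4.7% |
| Mechanical, p < 0.05 | 4.1-4.9% |
| No adjustment or any of four cut-offs (0.1, 0.2, 0.25, p < 0.05), whichever is significant | 6.5-7.0% |
| Discretion over which covariates with \|SMD\| > 0.1 count | 7.6-13.1% |

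In the last row the analyst may claim significance from no adjustment, from all covariates above 0.1, or from only those imbalanced in one direction or the other. Mechanical rules are conservative because the adjustment removes the large imbalances, while the prognostic variance of covariates left out stays in the residual error.

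**3. How far does the estimate move?**

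In the same simulation, adjusting at |SMD| > 0.1 rather than not adjusting moved the treatment estimate by 0.04-0.06 SD on average, with a 95th percentile of 0.09-0.15 SD. Against the conservative design effect of 0.4 SD in SAP 6.1, that is 10-15% on average (0.04/0.4 to 0.06/0.4) and about 22-38% at the 95th percentile (0.09/0.4 to 0.15/0.4).

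The simulation uses a simple linear model with simple randomisation, not the joint model with minimisation. It indicates the order of size only.

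**The case against.** The strongest reply is that very little is left open. The joint-model structure, five covariates, random effects and the contrast are all written down. A reader might infer that the primary model as a whole is chosen after seeing the data; SAP 7.1 does not support that, because only supplementary covariates are open. Nor does the rule reach every analysis. The Kaplan-Meier and log-rank comparison, the unadjusted proportions, and the hospital-day and outpatient summaries take no covariates. The Cox submodels list only intervention and the CDRS-R trajectory. All of this stands.

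A second reply is that being triggered is not the same as doing harm. A fixed cut-off is conservative, and the figures above 5% need an analyst who selects by result. The documents describe no such practice. That stands too: the inflation figures are a worst case and not a prediction.

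A third reply is that trigger rates rest on an assumed number of independent candidates, while likely ones, such as the symptom scales, overlap. A reader might infer that the rule would fire in most realisations of the trial. The numbers do not establish that. They start at 40% with 10 independent candidates, and are 23% with 5 and 29% with 10 correlated ones.

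What survives is that the criterion and the candidate list are absent, the judgement comes when outcomes are available, and no analysis in 7.1.2 is designed to vary the covariate set. Those sensitivity analyses vary the handling of missing data and of antidepressant use.

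**Conclusion.** The point holds as a gap in pre-specification and a poor basis for choosing covariates. The final covariate set of the primary model and the adjusted secondary models depends on an undefined judgement made after allocation is released.

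It does not follow that the rule by itself raises the false-positive rate. Applied mechanically with one cut-off, it gave 3.3-4.9%. The exposure comes from discretion: 6.5-7.0% if only the cut-off is free and 7.6-13.1% if the covariates are free as well. These figures rest on 5 or 10 independent candidates explaining 10-30% of outcome variance, which the documents do not give. Nor do the documents say that outcomes would be inspected before the choice; they simply do not prevent it.

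The change should be made, because the exposure bears on the primary p-value and is cheap to remove.

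**What to change.** - Delete the imbalance sentence from the Modeling paragraph of SAP section 7.
- Before unblinding, fix the covariates as the five named ones plus in-/outpatient type, with a stated coding for sites that offer only one kind of care.
- Keep the site random intercept in the primary model. Add site to the log-binomial and ANCOVA models in 7.2.1, which omit it. Their existing adjustment for baseline scores stays.
- Report any model with covariates selected on imbalance only as a labelled sensitivity analysis.

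The SAP is dated 23 May 2022, after the database closure that the Protocol synopsis planned for the end of April 2022. The documents do not say whether allocation had been released by then. If it had, the change should be dated and declared as made after release.

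The cost is one or two extra model terms (site may need several indicators if fitted as a fixed effect), a coding decision and one extra sensitivity analysis. No data, visits or sample size change.

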7.1 Primary endpoint

- CDRS-R total score from baseline (post-placebo-lead-in) to week 36

The primary analysis consists of a joint model linking (1) a linear mixed effects model for CDRS-R total score over time with (2) a Cox proportional hazards model for the risk of the event new initiation of or increase in antidepressant use (intervention dropout) and (3) a Cox proportional hazards model for the risk of study dropout as a competing event. This assumes that whether a participant has missing data and at what time this occurs contains additional information that should be taken into account and corresponds to an MNAR missing data mechanism.

Participants are censored at whichever occurs first of: antidepressant initiation/increase, loss to follow up, consent withdrawal, and study exit due to non-adherence. Participants lost to follow up, withdrawing consent, and exiting the study (as per protocol) due to non-adherence are considered alike and these events considered one event type: study dropout.

The linear mixed effects model for the longitudinal CDRS-R total score outcome $Y_i(t)$ measured at time t for participant i takes the following form:

$$\begin{aligned}
 Y_i(t) &= m_i(t) + \varepsilon_i(t), \\
 m_i(t) &= \beta_0 + \beta_1 \text{intervention}_i + \beta_2 t_{base} + \beta_3 t_{6weeks} + \beta_4 t_{12weeks} + \beta_5 t_{24weeks} + \beta_6 t_{36weeks} \\
 &\quad + \beta_7 t_{base} * \text{intervention}_i + \beta_8 t_{6weeks} * \text{intervention}_i + \beta_9 t_{12weeks} * \text{intervention}_i \\
 &\quad + \beta_{10} t_{24weeks} * \text{intervention}_i + \beta_{11} t_{36weeks} * \text{intervention}_i \\
 &\quad + \beta_{12} \text{age}_i + \beta_{13} \text{gender}_i + \beta_{14} \text{hsCRP}_i \\
 &\quad + \beta_{15} \text{antidepressant} + \beta_{16} \text{omega-3 index} \\
 &\quad + b_{i0} + b_{i1}t + b_{s0},
 \end{aligned}$$

where time t is considered a factor (while also investigating possibility of linearizing time effect) and randomized treatment group (intervention) and the interaction between randomized treatment group and time are included as fixed effects. The baseline values of the minimization factors age, gender, and hsCRP, as well as baseline antidepressant use and omega-3 index are included as covariates. The baseline outcome measure is modeled in the response, not as a covariate. The terms b_{i0} , b_{i1} , and b_{s0} represent participant-specific random intercepts and slopes and site-specific random intercepts. The random effects are assumed to be normally distributed and an unstructured covariance matrix will be assumed. The error term $\varepsilon_i(t)$ is assumed to be normally distributed with mean zero and variance σ^2 , independent of the random effects and is independent over time. An overall treatment effect for CDRS-R score at 36 weeks ($\beta_1 + \beta_{11}$) will be reported with a 95% confidence interval and corresponding p -value.

The competing survival models for time to event r (intervention dropout or study dropout) take the form:

$$\lambda_{ir}(t) = \lambda_{0r} \exp\{\gamma_1 \text{intervention} + \alpha_r m_i(t)\}$$

where the cause-specific Cox models include intervention as a time-independent effect and the estimated true trajectory of CDRS-R as a time-varying effect. The parameters α_r measure the strength of association between the longitudinal outcome and risk of the corresponding dropout event.

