Omega-3 Fatty Acids as First-Line Treatment in Pediatric Depression

Statistical Analysis Plan for [name], [name]

[name] ([contact])

[name]

Version 1.0 of May 23, 2022

List of abbreviations

AD	antidepressant
AE	adverse event
CDRS-R	Children's Depression Rating Scale - Revised
DIKJ	Children's Depression Inventory (Depressionsinventar für Kinder und Jugendliche)
EPA	eicosapentaenoic acid
KIDscreen-CAT-27	quality of life questionnaire
pMDD	pediatric major depressive disorder
SIQ-Jr	Suicide Ideation Questionnaire-Junior
SUSAR	Suspected Unexpected Serious Adverse Reaction

Introduction

1 Type of trial

This is a 36-week multi-center 1:1 randomized, double-blind, placebo-controlled, two-armed, parallel group study investigating the superiority of EPA-rich Omega-3 to placebo in the treatment of children and adolescents with pediatric major depressive disorder. The randomization included a minimization algorithm based on the following factors: site, age (8-12 vs. 13-18), gender (male vs. female), and hsCRP (<1 mg/l; 1-3 mg/l; >3mg/l). For sites offering both in- and out-patient care, in-/out-patient type was used as an additional minimization factor. The trial aimed to recruit children/teenagers between 8 and 18 years old with a primary diagnosis of major depressive disorder (DSM-IV, K-SADS-PL) and at least moderate depressive symptoms (CDRS-R ≥ 40).

In order to include a representative sample of moderately and severely ill children with major depressive disorders, the use of clinically required SSRIs is permitted. The anticipated proportion of patients receiving additional antidepressants at some point during follow-up is estimated to be around 30%. The use of additional antidepressants is expected to influence primary outcome measurements and be influenced by treatment group, with greater antidepressant use hypothesized in the control arm. Antidepressant use may therefore bias the estimation of the omega-3 treatment effect.

2 Scope of the statistical analysis plan

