4.1 Primary estimand

Effectiveness (i.e., 'de facto', 'treatment policy') estimand The effectiveness estimand quantifies the average treatment effect of EPA-rich Omega-3 relative to placebo over 36 weeks, as an adjunct to the German S3 guideline standard of care, in all randomized subjects regardless of adherence to treatment or initiation of antidepressants.

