4.2 Secondary estimand

Efficacy (i.e., 'du jure', 'hypothetical') estimand The efficacy estimand quantifies the average treatment effect of EPA-rich Omega-3 relative to placebo over 36 weeks, as an adjunct to the German S3 guideline standard of care, if all randomized subjects had adhered to the randomly assigned treatment for the entire trial duration.

5 Endpoints

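### The primary estimand (SAP 4.1) disregards antidepressant initiation, but the primary analysis (SAP 7.1) censors at it, so on its natural reading the week-36 contrast answers a different question

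*SAP*

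**What the plan says.** - **Primary estimand (SAP 4.1).** Treatment policy: the average effect over 36 weeks "in all randomized subjects regardless of adherence to treatment or initiation of antidepressants".
- **Secondary estimand (SAP 4.2).** Hypothetical: the effect "if all randomized subjects had adhered to the randomly assigned treatment for the entire trial duration". Added antidepressants are not mentioned.
- **Primary analysis (SAP 7.1).** A linear mixed model for CDRS-R is linked to two competing Cox models, one for antidepressant start or increase (called intervention dropout) and one for study dropout. "Participants are censored at whichever occurs first of: antidepressant initiation/increase, loss to follow up, consent withdrawal, and study exit due to non-adherence". The missingness is described as MNAR. The reported result is "An overall treatment effect for CDRS-R score at 36 weeks", with a confidence interval and p-value.
- **Population and dropout (SAP 7).** "The full analysis set (FAS) includes all randomized subjects". Study dropouts include participants who "are removed from the trial according to the protocol due to non-compliance".
- **Expected antidepressant use (SAP 1).** "The anticipated proportion of patients receiving additional antidepressants at some point during follow-up is estimated to be around 30" per cent, with more use expected on placebo. Protocol 5.2 (WH 2a) states the same direction as a hypothesis.
- **Sensitivity analyses (SAP 7.1.2).** Item 1 is the only analysis of the primary endpoint stated to use scores after antidepressant start. The SAP expects it to be biased in favour of placebo. Items 2 and 4 treat those scores as missing. Item 3, a complete-case analysis, is assigned to the efficacy estimand, and the SAP expects selection bias in it.
- **Follow-up (protocol 8.7.2).** Starting an antidepressant is not a reason for withdrawal.

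**The concern.** The event that the primary estimand says to disregard is the event at which the primary analysis stops following the participant. SAP 7.1 does not name the joint model's estimand, and protocol 11.4.1 describes that model as an intention-to-treat analysis. A reader will naturally attach the primary p-value to the primary estimand.

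At stake is the meaning of the main result. A treatment-policy effect describes what happens when omega-3 is offered and antidepressants are added as needed. A no-added-antidepressant effect describes omega-3 without that addition. The two differ whenever omega-3 changes antidepressant use, which the trial itself hypothesises.

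**Working it through.** **1. Does the longitudinal submodel use scores after antidepressant start?** SAP 7.1 does not say in words. These places all point to removal:
- Protocol 11.4.2: the time-to-event part is there because information is lost once an antidepressant is added.
- Protocol 6.3.2: counting antidepressant start as dropout in the joint model is meant to show whether omega-3 works on its own.
- SAP 7 (Missing data): starters are labelled dropouts.
- SAP 7.1.2, item 1: using later scores as observed is what sets that sensitivity analysis apart.
- SAP 7.2.1: the secondary analyses set data after intervention dropout to missing.

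The longitudinal model has only a baseline antidepressant term. The Cox parts address informative censoring; they do not bring later scores into the week-36 mean.

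**2. How many participants?** Inputs are from protocol 6.2 and SAP 1.
- Randomised: 225 + 20 = 245; with up to 20 more, 265.
- Expected to add an antidepressant: 0.30 × 245 = 73.5 and 0.30 × 265 = 79.5, so about 74 to 80.
- Protocol 6.3.2 reports about 20 starters before the week-6 visit: 20/225 = 8.9%, if counted at the same date. On the natural reading they contribute only a baseline score to the longitudinal submodel.

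**3. How far apart are the targets?** The plan gives no figure to reproduce. To first order, with the same benefit in both arms,

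policy effect = no-added-antidepressant effect − (placebo share − omega-3 share) × B,

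where B is the antidepressant benefit at week 36. Take 0.40 SD as the no-added-antidepressant effect (the planning value in SAP 6.1). Shares averaging 30% and B of 0.2 to 0.8 SD are assumptions.

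| Omega-3 / placebo share | Gap (SD) | Policy effect (SD) |
|---|---|---|
| 30% / 30% | 0 | 0.40 |
| 25% / 35% | 0.10 × 0.2 to 0.10 × 0.8 = 0.02 to 0.08 | 0.38 to 0.32 |
| 20% / 40% | 0.20 × 0.2 to 0.20 × 0.8 = 0.04 to 0.16 | 0.36 to 0.24 |

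**4. Does a censored-data contrast respond to what happens after antidepressant start?** Simulation with 200,000 per arm, start driven by the current score (29.9% placebo, 28.1% omega-3) and a true week-36 effect without added antidepressant of −5.0 points (−5.02 realised). The contrast came from data cut at antidepressant start, by sequential regression under MAR as a stand-in for the joint model.

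| Assumed benefit (points) | Policy effect | Censored-data estimate |
|---|---|---|
| 2 | −4.98 | −4.94 |
| 5 | −4.93 | −4.94 |
| 8 | −4.87 | −4.94 |

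The policy effect moves with the benefit and the estimate does not. That invariance is the finding. The closeness at 5 points is incidental, and the 0.08-point distance from −5.02 belongs to the stand-in. With use this similar by arm, the gap between targets is 5.02 − 4.98 = 0.04 to 5.02 − 4.87 = 0.15 points.

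**The case against.** The best defence has four parts.

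- **Censoring is survival-model language**, and SAP 7.1 never says that later CDRS-R scores are removed. This stands as a caution: removal is an inference, though a strong one. If the other reading is intended, 7.1 still needs the sentence, because two programmers could build different primary analyses.
- **Study dropout differs from antidepressant start.** A reader might infer that censoring at loss to follow-up or non-adherence exit also makes the target hypothetical. The documents do not support that. Protocol 8.4 ends participation at non-compliance, so later scores mostly do not exist and every estimand needs a missing-data assumption there. The conflict is clear only for antidepressant starters.
- **The SAP is open about the issue.** It discusses antidepressant bias, declares MNAR and reports an as-observed analysis. That is true, but nothing links that analysis to 4.1. Calling it biased is correct only against a no-added-antidepressant target, so the SAP marks down the analysis closest to its own primary estimand.
- **The gap may be small.** This also stands. The documents hypothesise the direction of the imbalance but give no size, and the larger gaps above need an assumed difference of 10 to 20 percentage points.

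**Conclusion.** The mismatch is real and needs correcting. The primary estimand includes what happens after antidepressant start; the primary analysis, on its natural reading, does not. The mapping is also poor for the efficacy estimand, which is tied to a complete-case analysis that the SAP itself expects to suffer selection bias.

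The number affected rests on the SAP's 30%. The size of the gap cannot be computed from the documents: it is zero if antidepressant use is balanced, probably small if use is similar by arm, and larger with the kind of imbalance the SAP hypothesises. Every gap above is an illustration on assumed values.

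Three stronger inferences are not supported:
- **A false-positive problem.** If omega-3 affects nothing, the two targets coincide, so the mismatch alone creates none.
- **A stated loss of power.** The documents do not allow the joint model's power to be bounded, and none is claimed here.
- **A second error in the SIQ-Jr analysis.** SAP 7.2.2 models it in the same way, but the SAP sets no estimand for it. Moreover, "Descriptive statistics for all efficacy and safety endpoints will be presented according to treatment arm", with no stated censoring.

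**What to change.** Make estimand and analysis agree, and record when this was done relative to unblinding. The SAP is dated 23 May 2022, after the database closure planned in the protocol synopsis (end of April 2022), and protocol 6.3.1 releases the code to the analyst after closure. The documents do not show whether the change could still precede unblinding.

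**Route A: keep the joint model and its p-value.**
1. Restate the primary estimand as the hypothetical week-36 CDRS-R difference in all randomised participants had none newly started or increased an antidepressant.
2. State in 7.1 that later scores leave the longitudinal submodel, and that study dropout, including non-adherence exit, is missing data under the joint model's assumption.
3. Make the present 4.1 text a secondary estimand estimated by sensitivity analysis 1, and say which target its expected bias refers to.
4. Map sensitivity analyses 2 and 4 to the hypothetical estimand.
5. Stop naming the complete-case analysis as the estimator of any estimand.

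The cost is SAP text and no new primary computation. It does change the stated primary question, so it should be declared as a change.

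**Route B: keep 4.1.** Make the mixed model on all observed scores primary, with a stated assumption for study dropouts. Rewrite 4.2 as the no-added-antidepressant estimand before assigning the joint model to it; as written, 4.2 concerns full adherence, so assigning the model to it would create a new mismatch. This route changes the primary analysis in protocol 11.4.1 and 11.4.2 and may need an amendment under protocol 2.10.

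Optional in either case: one SIQ-Jr mixed model, as randomised, on every observed score without censoring at antidepressant start.
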